6.17.2. Hematology

Hematology should include assessment of the following: hemoglobin, hematocrit, red blood cell count, white blood cell count with differential, and platelet count.

6.17.3. Serum Chemistries

Serum chemistries (non-fasting) should include assessment of the following: alkaline phosphatase, albumin, alanine aminotransferase (ALT), AST, CPK, blood urea nitrogen (BUN), creatinine, creatinine clearance, glucose, lactate dehydrogenase, total and direct bilirubin, total protein, sodium, serum calcium (corrected calcium), phosphate, magnesium, and potassium. For calculated creatinine clearance, see Appendix I.

6.17.4. Coagulation Panel

Serum coagulation panel should include assessment of the following: prothrombin time (PT)/international normalized ratio (INR) and activated prothrombin time (PTT).

6.17.5. Thyroid Function Tests

Thyroid function tests should include assessment of the following: thyroid stimulating hormone (TSH) and free tetraiodothyronine (free T4). Triiodothyronine (T3) may be obtained as a reflexive test if considered necessary by the Investigator based on local practice.

6.18. Pharmacokinetic Samples: Blood

For PK sample collection regimen and schedule, please refer to sub-protocols.

6.19. Disease Assessment

6.19.1. Tumor Measurements

Disease assessment must be conducted in accordance with the Imaging Manual. Tumors will be assessed by radiographic tumor measurements using computed tomography (CT) and/or MRI (as indicated).

CT/MRI must be performed within 28 days prior to the first dose of study drug during screening. To ensure image consistency, the same imaging modalities and acquisition protocols used at screening are to be used for subsequent tumor assessments.

Investigators must conform to the CT and/or MRI acquisition requirements specified in the Imaging Manual consistently for all patients throughout the study. Disease assessments will

use RECIST version 1.1 or RANO criteria, as clinically appropriate (see Appendix B and Appendix C).

6.19.1.1. Collection of Radiographic Studies for Independent Review

Baseline screening radiographic studies and all subsequent radiographic studies will be collected and stored for independent radiological review.

Identification of radiographic findings that may affect patient management or outcomes during the course of patient participation in the study are the responsibility of the treating physician. Independent radiology review for this trial is only used to assess the objectives of the study. Any unexpected medical findings identified during subsequent independent radiologic review will not be reported back to the Investigator.

6.20. Telephone/Telemedicine Visit

The site will contact the patient or the patient's parent/legal guardian by telephone for telephonic/telemedicine visits to assess for tolerability, continuation of study drug, and whether the patient needs to return to clinic earlier than planned. The patient or the patient's parent/legal guardian should be contacted regularly to assess AE status.

6.21. Survival Status

Patients will be followed for survival status, date of progression, and subsequent anticancer therapies by telephone or any other method.

6.22. Study Drug Administration and Dosing Diary

Completion of the outpatient dosing diary will include recording of study drug dosing.

6.23. Concomitant Medication

All medications that were used from 28 days prior to enrollment through 30 days following the last dose of study drug will be recorded in the eCRF.

6.24. End of Treatment Visit

EOT is defined as Day 28 (\pm 7 days) of the final cycle of treatment (or time of premature discontinuation of treatment). The EOT assessments and procedures will be conducted in accordance with the Schedule of Activities in the relevant sub-protocol.

6.25. Safety Follow-up Visit

Safety follow-up assessments may be performed as part of the EOT visit if the latter was performed at least 28 days after final dose of the last cycle. The safety follow-up visit may be conducted by telephone if patient is not able to return to clinic.

6.26. Long-Term Follow-up

After study treatment discontinuation, LTFU assessments will occur approximately every 3 months (\pm 1 month) until the patient withdraws consent for further participation, is lost to follow-up, has died, or the study is closed. For any patient who discontinues study treatment prior to disease progression, tumor assessment will progress accordingly as if on study treatment and will be requested to return to site for continued monitoring and assessment. After progression and in LTFU, the site will contact the patient or the patient's parent/legal guardian for follow-up assessments that may include subsequent anticancer therapies and survival status. LTFU may be conducted by telephone except for those patients who have not yet progressed after treatment discontinuation. For any patient who is lost to follow-up, the study site will attempt to ascertain survival information via public database search. If survival status still cannot be ascertained, patients will be considered lost to follow-up. The first LTFU assessment will occur 3 months (\pm 1 month) after the EOT visit.

6.27. Force Majeure Flexibility

With the outbreak of severe acute respiratory syndrome coronavirus 2 (SARS-CoV-2) and the impact of coronavirus disease 2019 (COVID-19) on the health-care system, the Sponsor of this study recognizes the need for flexibility in ensuring access to therapy. This need has been clearly elucidated in the FDA Guidance on Conduct of Clinical Trials of Medical Products during COVID-19 Public Health Emergency (FDA-2020-D-1106) and the EMA Guidance on the Management of Clinical Trials during the COVID-19 (Coronavirus) pandemic (Version 3, 28/04/2020). While every effort should be made to follow the timing of study visits and procedures as closely as possible, the Sponsor may introduce flexibility in the nature and timing of visits. Changes may include using home health-care visits, telemedicine visits, local imaging, and distribution of multiple cycles of investigational product (or shipping investigational product to a patient's residence).

If such flexibility needs to be implemented for the safe conduct of this study, the Sponsor will notify sites of what procedures may be delayed or provide flexibility in how data are collected. As potential impacts to the health-care system may not be uniform through all regions where the Sponsor is conducting this study, guidance will be informed by worldwide regulatory authority guidance and local competent and ethical authorities and may vary from site to site. Changes to timing and procedures will be communicated by the Sponsor through an official memo and training.

7. PLANNED ANALYSES

A statistical analysis plan (SAP) will be prepared and finalized prior to database lock for each sub-protocol. This document will provide further details regarding the definition of analysis variables and analysis methodology to address all study objectives. Any deviations in the planned analysis as stated in the protocol will be delineated in the SAP. Any deviations from the SAP will be reported in the clinical study report.

7.1. Analysis Populations

The populations for analysis are defined in Table 7.

Table 7: Population Definitions

Population	Description
Efficacy	All patients who received at least 1 dose of study drug and have measurable disease as determined by the Investigator at baseline and have at least 1 follow-up imaging or radiographically confirmed progressive disease prior to the first imaging timepoint (FAS)
Safety	All patients enrolled in the study who received at least 1 dose of study treatment (SAS)
DLT	Patients enrolled in a safety run-in cohort, received at least 1 dose of study treatment, and completed 75% of dosing in Cycle 1, unless discontinued for toxicity

Abbreviations: DLT, dose-limiting toxicity; FAS, Full Analysis Set; SAS, Safety Analysis Set.

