Please see relevant sub-protocols for radiology review procedures and tumor specimen collection procedures.

End of Study and Length of Study:

Please refer to relevant sub-protocol for information on duration of each study and end of study information.

STATISTICAL METHODS:

Sample Size Considerations:

Please see sub-protocols for sample size considerations relevant to each sub-protocol. Additional patients will be enrolled to account for any patients who are lost to follow-up or have no follow-up imaging.

Analysis Methods:

Efficacy Analyses

All efficacy analyses will be performed on the full analysis set (FAS) population, which includes all patients who received at least 1 dose of study drug and have measurable disease as determined by the Investigator at baseline and have at least 1 follow-up imaging or radiographically confirmed progressive disease prior to the first imaging timepoint as outlined in Section 7.3.1.

Overall response rate (ORR) as assessed by the proportion of patients with the best overall confirmed response of complete response (CR) or partial response (PR), according to the appropriate tumor response criteria as assessed by Investigator will be calculated and an exact confidence interval (CI) will be calculated. Duration of response (DOR) in patients with best overall response of CR or PR defined as from time of first tumor response to progression or date of data analysis, whichever occurs earlier as determined by the Investigator will be calculated. Progression free survival (PFS) is defined as the time from the date of the first dose of study drugs to the first occurrence of disease progression according to the appropriate tumor response criteria as assessed by Investigator, or death from any cause, whichever occurs earlier. Overall survival (OS) is defined as the period from the date of the first dose of study drugs until the date of death from any cause. Kaplan-Meier curves will be plotted for DOR, PFS, and OS. The timepoint for the analysis of response for Phase 2 studies' primary efficacy objective will be when all patients have a minimum of 6 months of follow-up.

Safety Analyses

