7.2. Determination of Sample Size

For methods related to determination of sample size, refer to specific sub-protocols. Additional patients will be enrolled to account for any patients who are lost to follow-up or have no follow-up imaging.

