7.3.1. Efficacy Analyses

The efficacy analyses will be performed on the full analysis set (FAS) population which includes all patients who received at least 1 dose of study drug and have measurable disease as determined by the Investigator at baseline and have at least 1 follow-up imaging or radiographically confirmed progressive disease prior to the first imaging timepoint.

ORR as assessed by the proportion of patients with the best overall confirmed response of CR or PR, according to the appropriate tumor response criteria as assessed by Investigator will be calculated and an exact CI will be calculated. DOR in patients with best overall response of CR or PR as determined by the treating Investigator defined as from time of first tumor response to progression or date of data analysis, whichever occurs earlier will be calculated. PFS is defined as the time from the date of the first dose of study drugs to the first occurrence of disease progression according to the appropriate tumor response criteria as

assessed by Investigator, or death from any cause, whichever occurs earlier. OS is defined as the period from the date of the first dose of study drugs until the date of death from any cause. Kaplan-Meier curves will be plotted for DOR, PFS, and OS. TTR in patients with best overall response of CR or PR will be determined by the treating Investigator from the initiation of study treatment to the date of first response. The timepoint for the analysis of response for Phase 2 studies' primary efficacy objective will be when all patients have a minimum of 6 months of follow-up.

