### **2.2.2. Sample Size and Power**

The number of patients is determined by using Simon's 2-stage design (Simon 1989).

A large black rectangular box covers the majority of the page below the text, indicating that the sample size and power information has been redacted.

Patients are considered efficacy-evaluable if they received at least 1 dose of study drug and have measurable disease by investigator assessment at baseline. Efficacy-evaluable patients who don't have post-baseline disease assessment will be considered as non-responders.

Sample size determination for each cohort is specified in Table 1.

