## **3.2. Analysis Sets and Subgroups**

### **3.2.1. Efficacy Analysis Set**

All patients who receive at least one dose of tovorafenib and have measurable disease as determined by the Investigator at baseline will be considered evaluable for efficacy and included in the Efficacy Analysis Set. Efficacy-evaluable patients who don't have any post-baseline disease assessment will be considered as non-responders.

Patients in the Efficacy Analysis Set who have a best overall confirmed response of CR or PR will be evaluable for duration of response (DOR) and time to response (TTR).

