## 4. DEVIATIONS FROM PROTOCOL

Definition of efficacy analysis sets, Section [3.2.1](#).

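### The master protocol leaves treated patients who are never imaged out of ORR, PFS and OS and enrols others to account for them; the 102a SAP corrects the set, but the master text does not

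*Protocol*

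**What the plan says.** **Master protocol.** Table 7 (Section 7.1) sets three conditions for the efficacy population, called the FAS: at least one dose, measurable disease at baseline by the Investigator, and a post-dose condition, namely that patients "have at least 1 follow-up imaging or radiographically confirmed progressive disease prior to the first imaging timepoint (FAS").

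The synopsis states: "All efficacy analyses will be performed on the full analysis set (FAS) population". Section 7.3.1 says the same ("The efficacy analyses will be performed on the full analysis set (FAS) population"), defines ORR, DOR, PFS and OS under that set, and adds that "Kaplan-Meier curves will be plotted for DOR, PFS, and OS". It names no other population for any of them. PFS and OS both run from first dose, and death from any cause is an event in each.

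Section 7.2 and the synopsis also state: "Additional patients will be enrolled to account for any patients who are lost to follow-up or have no follow-up imaging". They give no number or limit.

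**102a SAP.** Section 3.2.1 has no imaging condition. Patients who receive a dose and "have measurable disease as determined by the Investigator at baseline will be considered evaluable for efficacy and included in the Efficacy Analysis Set". Section 2.2.2 adds: "Efficacy-evaluable patients who don't have post-baseline disease assessment will be considered as non-responders". Section 4 declares the change in one line, "Definition of efficacy analysis sets, Section" 3.2.1. SAP Appendix 6.3 counts a death without documented progression as a PFS event unless it follows two or more missed assessment visits. It censors at first dose patients with no post-baseline assessment who have neither progressed nor died.

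**The concern.** Membership of the efficacy set depends on something that happens after dosing. The patients who fail the condition are not a random sample: they include early deaths without imaging, along with withdrawals and losses. Removing them takes non-responders out of the ORR denominator and early deaths out of PFS and OS.

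For ORR one could at least argue that response cannot be assessed without a scan. That argument is not available for OS. Protocol Sections 6.21 and 6.26 collect survival status by telephone and, for patients lost to follow-up, by public database search. A treated patient who dies in week 5 has a fully observed OS time, and the set discards it.

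The enrolment sentence adds to this. If unimaged patients are made up until the planned number of imaged patients is reached, a response cut-off chosen for the true rate is applied to the inflated rate.

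**Working it through.** **Inputs.** The plan gives no figure to reproduce. The master protocol leaves sample size to the sub-protocols, and the hypotheses, error rates, sizes and cut-offs in SAP Table 1 are redacted. The excluded fraction u is not stated and is assumed to be 5% to 20%.

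**Who leaves the set.** Taking treated patients with measurable disease at baseline:
- Radiographically confirmed PD before the first imaging timepoint: stays in (Table 7).
- Stops treatment before progression and is scanned later: stays in. Section 6.26 continues tumour assessment as if on treatment, and Appendix B asks for efforts to document progression after discontinuation.
- Dies, withdraws or is lost with no post-baseline imaging: leaves ORR, PFS and OS.

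**ORR.** Excluded patients cannot have a confirmed response, so with R responders among N treated patients the true rate is R/N and the FAS rate is R/[N(1-u)] = ORR/(1-u).

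| True ORR | u = 5% | 10% | 15% | 20% |
|---|---|---|---|---|
| 20% | 21.1% | 22.2% | 23.5% | 25.0% |
| 30% | 31.6% | 33.3% | 35.3% | 37.5% |

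Example: 6 responders among 30 treated patients, 3 of them unimaged. The SAP set gives 6/30 = 20.0% (exact 95% CI 7.7 to 38.6). The master FAS gives 6/27 = 22.2% (8.6 to 42.3).

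**OS, upper bound.** Assume exponential survival, a first scan at week 8 (the schedule is redacted; 56/30.4375 = 1.84 months) and no imaging before any death that precedes it. The excluded fraction is 1 - exp(-ln 2 × 1.84/m) for median m. Because the exponential has no memory, the median among those remaining is m + 1.84.
- m = 6 months: 19% excluded, reported median about 7.8 months (+31%).
- m = 12 months: 10% excluded, reported median about 13.8 months (+15%).

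**PFS.** The direction is the same and comes from the early deaths. If the Appendix 6.3 rule applied, unimaged patients who neither died nor progressed would be censored at first dose and contribute no PFS time whether included or not. The PFS bias is not quantified here.

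**Error rates when unimaged patients are made up.** This uses an assumed Simon design, not the trial's own: null 10%, alternative 30%, continue if more than 1 of 10 respond, success if more than 5 of 29 respond. With make-up to the planned n, p becomes p/(1-u).

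| u | Type I error | Apparent power |
|---|---|---|
| 0 | 4.7% | 80.5% |
| 5% | 5.8% | 84.1% |
| 10% | 7.1% | 87.3% |
| 15% | 8.8% | 90.3% |
| 20% | 11.0% | 92.8% |

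Changing the denominator alone is not enough if patients are still added and the cut-off stays fixed. Ignoring the stage 1 stop, the chance of at least 6 responses at a true 10% is 6.4% for N = 29 and 10.6% for N = 33 (29/0.9 = 32.2, rounded up).

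**The case against.** The strongest reply is that the only SAP in the file has already fixed this. It drops the imaging condition, counts unimaged patients as non-responders, declares the deviation where protocol Section 7 says such changes belong, and generally counts early deaths as PFS events. That stands: the bias does not reach the 102a ORR. The study was also terminated early, and its interim and primary analyses will not be performed (SAP 2.2.1, 2.3.1, 2.3.2).

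The excluded group is also narrower than Table 7 suggests at first sight. A reader might infer that early failures in general leave the set. They do not: early radiographic PD is kept, and patients who stop for toxicity or clinical deterioration leave only if they are never scanned.

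Three further readings are tempting, and the documents do not support them.
- That the additional-enrolment rule still operates in 102a and upsets the response counts in SAP Table 1. The SAP's sample-size text and that table are redacted, the sub-protocols are not in the file, and SAP Section 4 is not where enrolment would be amended. After termination, the planned efficacy output is ORR with an exact interval, not a test against those counts.
- That 102b will report ORR on a different denominator. Each sub-protocol has its own SAP, and the one for 102b is not available.
- That the 102a SAP should state that unimaged patients are not replaced. Nothing available shows whether any were.

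Finally, enrolling patients to account for losses may mean a general attrition allowance and not one-for-one replacement. The sentence allows both readings, which is itself a reason to clarify it.

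**Conclusion.** The point holds for the master protocol. Table 7, Section 7.3.1 and the synopsis exclude treated patients with measurable disease who have neither a post-baseline scan nor radiographically confirmed PD, and Section 7.2 and the synopsis add patients to account for those without imaging. The direction of bias is upward for ORR, PFS and OS. For ORR the size is exactly 1/(1-u), so a true 30% appears as 31.6% to 37.5% for u between 5% and 20%; only u is assumed. The OS figures (+31% and +15% on the median) are upper bounds that also rest on exponential survival, an 8-week first scan and all pre-scan deaths being unimaged. The error-rate figures illustrate an assumed design and say nothing about the trial's redacted one.

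For 102a the analysis set is already corrected. What remains is the master text and any other sub-protocol that inherits it without an override.

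**What to change.** - **Table 7, Section 7.3.1 and synopsis:** adopt the SAP 3.2.1 set, that is, at least one dose and measurable disease at baseline, with no post-baseline assessment counted as non-response in ORR.
- **PFS and OS:** measure both from first dose in that set, and state that a death before any scan is an event in each. State also how unimaged patients who have not died are censored for PFS, since the SAP rule gives them no PFS time.
- **Section 7.2 and synopsis:** delete the additional-enrolment sentence, or limit it to patients never dosed or without measurable disease at baseline. If patients are added for any reason, tie the response cut-off to the actual N.

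The cost is wording in Table 7, Sections 7.2 and 7.3.1 and the synopsis. No new data are needed, and the set is one the sponsor has already adopted for 102a. The downside is that ORR, PFS and OS become less favourable, and the apparent gain in power from excluding unimaged patients is lost.

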3. INVESTIGATIONAL PLAN

3.1. Study Design

This is a Phase 1b/2, multi-center, open-label, umbrella study of patients \geq 12 years of age with recurrent or progressive solid tumors with alterations in the key proteins of the RAS/RAF/MEK/ERK pathway, which will be referred to as the MAPK pathway. Patients with these alterations will be identified through molecular assays as routinely performed at Clinical Laboratory Improvement Amendments of 1988 (CLIA) or other similarly certified laboratories.

Based on the identified alterations in the key proteins of the MAPK pathway, patients may be offered the opportunity to participate in one or more sub-protocols within this umbrella study of DAY101 as monotherapy or in combination with other therapies. Enrollment will be based on the specific eligibility criteria described in each sub-protocol.

Study DAY101-102 (master study) and sub-protocols consist of a screening period, a treatment period, a safety follow-up period, and a long-term follow-up (LTFU) period where survival status, and subsequent anticancer therapies will be collected.

DAY101 will be administered as specified in the sub-protocol. Additional dose schedules may be explored. Dose level(s), dose schedule(s), and cycle lengths for DAY101 as monotherapy or in combination with other therapies will be specified in each sub-protocol.

Cycles will repeat, as specified in each sub-protocol, until disease progression, unacceptable toxicity, withdrawal of consent, or death.

Patients will undergo radiographic evaluation of their disease at baseline, at the end of [REDACTED] for 1 year and then [REDACTED] thereafter, or as specified in a given sub-protocol. Generally, response assessment will be performed according to Response Evaluation Criteria in Solid Tumors (RECIST) version 1.1 for solid tumors. Alternative criteria may be used in specific disease settings, such as glioma, where response assessment will be assessed by RANO criteria. Appropriate response criteria for tumors are described in Appendix B and Appendix C.

[figure not shown]
Patients who have radiographic evidence of disease progression may be allowed to continue DAY101 (and combination partner if applicable) if, in the opinion of the Investigator, the patient is deriving clinical benefit from continuing study treatment, and continuation of treatment is approved by the Sponsor.

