5.2.2. Dose-Limiting Toxicity

Assessment of DLT will be further specified in relevant sub-protocols.

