5.3. Removal of Patients from Therapy or Assessment

Patients may withdraw from the study at any time. Patients who withdraw from therapy and do not withdraw consent will be referred to as “discontinue study treatment” and will be followed for LTFU. Over the course of the study, a patient may discontinue from study treatment for any of the reasons listed below:

- Disease progression as assessed by the Investigator, except if, in the opinion of the Investigator and with permission of the Sponsor, the patient is deriving clinical benefit from continued study treatment
- Unacceptable toxicity
- Intercurrent illness compromising the ability to fulfill protocol requirements
- Dosing interruption > 28 days, unless resumption of treatment approved by the Sponsor
- Requirement for alternative treatment in the opinion of the Investigator
- Significant noncompliance to protocol
- Pregnancy
- Withdrawal of consent or assent by the patient or the patient’s parent or legal guardian
- Loss to follow-up
- Death

When a patient discontinues from treatment, the patient will undergo the end of treatment (EOT) visit, as outlined in Section 6.24 .

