6. TESTS AND EVALUATIONS

All required observations and schedules are described in more detail in Sections 6.1 through 6.27.

Most study assessments and procedures (including treatment administration) will be performed in cycles, defined as 28-day intervals starting with the date of DAY101 administration at baseline unless otherwise specified in the sub-protocol. In the absence of toxicity, all scheduled visits will occur within windows for the protocol-specified visit schedule. If the patient is unable to have a study assessment within the defined time window due to an event outside of his or her control (e.g., clinic closure or travel restrictions due to COVID-19, personal/family emergency, inclement weather), the assessment should be performed as close as possible to the required schedule.

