8.2. Data Monitoring Committee (DMC)

An independent Data Monitoring Committee (DMC) will be established to oversee the safety aspects of the study and to render dose safety decisions as applicable based on sub-protocol (see Section 8.2.1).

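### The Table 7 DLT population can drop a patient who had a DLT if the event was managed by holding doses, which could bias run-in DLT incidence downward

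*Protocol*

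**What the plan says.** Table 7 in Protocol Section 7.1 defines the DLT population as patients in a safety run-in cohort who "received at least 1 dose of study treatment, and completed 75% of dosing in Cycle 1, unless discontinued for toxicity". It is the only DLT population in the supplied documents. Protocol Section 2 (Table 5) lists DLT incidence among the endpoints for the Phase 1b primary objective on MTD and RP2D, and confines Phase 1b to combination sub-studies.

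The other relevant provisions are:

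- **Schedule.** Protocol Section 5.2.1 describes weekly dosing. Section 6 has cycles "defined as 28-day intervals starting with the date of DAY101 administration at baseline", unless a sub-protocol says otherwise. Section 3.1 adds: "Dose level(s), dose schedule(s), and cycle lengths for DAY101 as monotherapy or in combination with other therapies will be specified in each sub-protocol".
- **Interruption and discontinuation.** Protocol Section 5.3 includes among the reasons for stopping treatment "Dosing interruption > 28 days, unless resumption of treatment approved by the Sponsor". SAP Sections 3.6.1 and 3.8.2 report interruptions and discontinuations as separate categories.
- **What is deferred.** Protocol Section 5.2.2 says "Assessment of DLT will be further specified in relevant sub-protocols". Sections 5.2.3 and 5.2.4 defer dose modification and toxicity management in the same way.
- **Room to depart.** Protocol Section 7 says "Any deviations in the planned analysis as stated in the protocol will be delineated in the SAP". The SAP for 102a uses this once, in its Section 4, for "Definition of efficacy analysis sets". That SAP has no DLT set.

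**The concern.** A minimum-exposure rule is meant to remove patients who were too lightly dosed to show whether the regimen is tolerable. A patient who has had a DLT has already given that answer, however few doses were taken. Table 7 rescues such a patient only if treatment was discontinued for toxicity. If the DLT was handled by holding doses and then resuming, no clause applies.

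Whether a DLT counts then depends on how it was managed, and the patients removed by this route all have the event. DLT incidence for a combination dose could look lower than it is, on an endpoint that serves the Phase 1b primary objective.

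**Working it through.** The plan gives no DLT rate, run-in size or hold frequency, so there is no figure of its own to reproduce. The check has four steps.

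**1. Who falls below 75%.** Weekly dosing (Protocol 5.2.1) in a 28-day cycle (Protocol 6, default) gives 28/7 = 4 Cycle 1 doses.

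| Doses held | Share completed | Status under Table 7 if treatment then resumes |
|---|---|---|
| 0 | 4/4 = 100% | in |
| 1 | 3/4 = 75% | in |
| 2 | 2/4 = 50% | out |
| 3 | 1/4 = 25% | out |

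Only a DLT arising before the third dose can cost two or more Cycle 1 doses. One arising after dose 3 can cost at most one.

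**2. Whether the hold counts as discontinuation.** Section 5.3 lists an interruption only when it exceeds 28 days. On this schedule, the longest case is a patient who takes dose 1 on Day 1, misses the other three, and restarts on Day 29. The gap between doses is 29 − 1 = 28 days, which does not exceed 28. A patient who misses only doses 3 and 4 has a gap of 29 − 8 = 21 days. Neither meets that criterion, so the Table 7 exception does not apply on the documents' own usage.

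**3. Effect of one exclusion (exact, with no assumed rates).** Removing one DLT patient changes x/n to (x−1)/(n−1). The difference is (x−n)/[n(n−1)], which is negative whenever x < n. The cohort sizes below are examples, not taken from the plan.

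| With the patient | Without | Change (points) |
|---|---|---|
| 1/3 = 33.3% | 0/2 = 0% | −33.3 |
| 1/6 = 16.7% | 0/5 = 0% | −16.7 |
| 2/6 = 33.3% | 1/5 = 20.0% | −13.3 |

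**4. Expected rate (illustration; p, f and g are all assumptions).** Let p be the true DLT rate, f the share of DLT patients excluded, and g the share of patients without a DLT who are excluded. The expected rate in the Table 7 population is

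q = p(1−f) / [p(1−f) + (1−p)(1−g)].

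| p | g | f = 10% | f = 25% | f = 50% |
|---|---|---|---|---|
| 20% | 0 | 18.4% | 15.8% | 11.1% |
| 30% | 0 | 27.8% | 24.3% | 17.6% |
| 40% | 0 | 37.5% | 33.3% | 25.0% |
| 30% | 10% | 30.0% | 26.3% | 19.2% |

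Example: p = 30%, f = 25%, g = 0 gives 0.225/(0.225 + 0.70) = 0.225/0.925 = 24.3%. When f = g the two exclusions cancel and there is no net bias. The rate is biased low when f exceeds g.

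**The case against.** The strongest objection is that the setting where this matters lies in documents not supplied. DLT assessment, dose modification, schedule and cycle length for combinations all belong to sub-protocols. A combination sub-protocol may already count every DLT, may use a different number of Cycle 1 doses, or may require discontinuation after the kind of DLT described, in which case the existing exception keeps the patient. Its SAP may also override Table 7. All of this stands. It limits what can be claimed to the master definition as written, but deferring how a DLT is assessed does not by itself change who Table 7 admits.

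Second, the exception could be read more loosely, so that any stop in Cycle 1 dosing caused by toxicity counts. The 28-day item in Section 5.3 covers interruptions of any cause, and unacceptable toxicity is a separate item with no time limit. The looser reading is possible, but the SAP keeps interruption and discontinuation apart, and the population for a primary-objective endpoint should not rest on an unstated reading.

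Third, the affected group is narrow: early DLTs, at least two doses held, treatment resumed. The size of the bias is hypothetical. Both points are correct.

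Fourth, the event is not lost. It remains in the Safety set, general adverse-event data also serve the MTD/RP2D objective, and the data monitoring committee is there "to render dose safety decisions as applicable based on sub-protocol". This softens the consequence but leaves the reported DLT incidence wrong.

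**Conclusion.** The concern holds. Read literally, Table 7 excludes a run-in patient who has a DLT, misses two or more of four weekly Cycle 1 doses and resumes. One such exclusion lowers the observed rate unless every patient had a DLT; in an example cohort of six, by 16.7 points when there is one DLT and 13.3 points when there are two. The expected bias cannot be estimated from the supplied documents.

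The conclusion rests on the master default of four doses, on reading discontinuation as distinct from interruption, and on no combination sub-protocol or SAP overriding Table 7. A net downward bias also requires DLT patients to be excluded more often than the others. It bears on combination run-ins only; the 102a analysis does not use this population. It should be fixed, with medium confidence because the governing sub-protocols could not be checked.

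**What to change.** Redefine the DLT population in Table 7 as run-in patients who received at least one dose of study treatment and either (a) had a DLT in the assessment window, regardless of the share of doses taken, or (b) had no DLT and completed at least 75% of Cycle 1 dosing. The window should be the one set in the combination sub-protocol, since the supplied documents do not state it; Cycle 1 is the natural reading of Table 7. Reconcile the wording with that sub-protocol's own definition of DLT-evaluable patients. At the same time, state whether the 75% counts doses or milligrams, and whether it applies to DAY101, the partner drug or both, because Table 7 leaves this open.

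If the master protocol is not amended, declare the definition as a deviation in the combination sub-protocol's SAP, as Protocol Section 7 allows.

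The cost is one line of protocol text or one SAP entry, with no added patients or procedures. The downside is a modest upward tilt, because all DLTs count while under-dosed patients without one are still excluded. With a true rate of 30% and 10% of patients without a DLT excluded, the expected rate is 0.30/(0.30 + 0.70 × 0.90) = 0.30/0.93 = 32.3%.
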